**Effects of intermittent caloric restriction in youth with
cardiometabolic risk: a randomized controlled pilot study**

Supplementary Research Ethics Board Approval

NCT number: NCT04011995

September 20, 2019

**Effects of intermittent caloric restriction in youth with cardiometabolic risk:
a randomized controlled pilot study**

Supplementary Research ethics board approval

This is a randomized controlled pilot study to evaluate the effects of intermittent caloric restriction compared with low carbohydrate diet in youth with cardiometabolic risk. Total trial duration for individual subject is one month consisting of a 14-day intervention phase and a 14-day self-maintenance phase.

In the previous study protocol, the eligible subjects were defined as pre-diabetic youth aged 13 to 30 years old which were high risk population for cardiometabolic diseases. The study was approved by the Research Ethics Committee of the Children's Hospital of Fudan University (CHFU 2017 No. 228) in December 2017.

In 2019, we adjusted the inclusion criteria and expanded the age range of the eligible subjects after discussion by the study team.

The adjusted inclusion criteria are as follows:

- (1) Aged 9-30 years old;
- (2) With at least one of the following cardiometabolic risk:
 - Overweight or obesity (central obesity or general obesity);
 - Prediabetes: impaired fasting glucose and/or impaired glucose tolerance;
 - Dyslipidemia;
 - Elevated blood pressure.

The previous subjects and the adjusted subjects were from the same population, and previous subjects were part of the adjusted study subjects. The protocol after adjusting the subjects was also approved by the Research Ethics Committee of the Children's Hospital of Fudan University (CHFU 2019 No. 216) in June 2019.

RESEARCH ETHICS BOARD APPROVAL

PROTOCOL TITLE: Effects of Intermittent Caloric Restriction on Glucose Regulation and Related Gene Methylation in Youth Pre-diabetic Youth

PRIMARY INVESTIGATORS: [name] PROTOCOL TYPE: Lifestyle intervention study

APPLICATION INSTITUTIONS: Children's Hospital of Fudan University

STARTING AND ENDING DATES: 2018.1—2020.12

NAME LIST OF RESEARCH ETHICS BOARD: [name]; [name]; [name]; [name]; [name]; [name]; [name]; [name]; [name]; [name]

THE FOLLOWING ITEMS ARE COMPLETED BY RESEARCH ETHICS BOARD:

DOCUMENTS: (CLICK ✓ BEFORE OPINION)

(✓) protocol
(✓) application form
(✓) informed and consent form
() relevant approvals

## **1. Introduction**

The purpose of this Statistical Analysis Plan (SAP) is to define the outcome variables, statistical methods, and analysis strategies to address the objectives in the randomized, controlled pilot trial for effects of intermittent caloric restriction in youth with cardiometabolic risk.

This study is a randomized controlled pilot trial of intermittent caloric restriction versus low carbohydrate diet in youth with cardiometabolic risk over one month period. The experimental intervention is based on the 5:2 diet, which involves caloric restriction for 2 days (consecutive or nonconsecutive, 600 kcal/d for male and 500 kcal/d for female) per week and unrestricted eating during the other 5 days of the week. For control group, the subjects receive 7 days (consecutive or nonconsecutive) of low carbohydrate diet intervention during the 14-day intervention period. Carbohydrate intake of low-carbohydrate diet should be controlled as  $\leq 50$  g per day. Total trial duration is one month consisting of a 14-day intervention phase and a 14-day self-maintenance phase. Follow-up electronic questionnaires were conducted during the maintenance phase.

## **2. Study objectives and outcomes**

### **2.1. Study objectives**

#### **2.1.1. Primary objective**

The primary objective is to evaluate the reversal of cardiometabolic abnormality between intermittent caloric restriction and low carbohydrate diet in youth after 14-day intervention phase.

#### **2.1.2. Secondary objectives**

To make these comparisons between the two groups from the baseline (the first day of the intervention phase) to the 14th day of the intervention phase or the 14th day of the self-maintenance phase:

- (1) Change in insulin.
- (2) Change in insulin-like growth factor-1.
- (3) Change in mean blood glucose.
- (4) Change in gut microbial compositions.
- (5) Change in body weight.
- (6) Change in waist circumference.

## 2.2. Outcomes

### 2.2.1. Primary outcome

#### **Reversal (%) of cardiometabolic abnormality.**

The primary outcome is a composite outcome that will be measured as any reverse ~~outcome~~ of the following cardiometabolic abnormality: (1) overweight or obesity, (2) prediabetes, (3) hyperlipidemia or (4) elevated blood pressure. It is defined as occurring if any cardiometabolic abnormality of individual subject has a reversal outcome after 14 days dietary intervention (measured at the 14th day).

The primary endpoint will be summarised by number (%) of subjects that with at least one reverse of cardiometabolic abnormalities.

#### **Reversal of cardiometabolic abnormality is defined as:**

At the 14th day of dietary intervention phase, at least one of the following indicators changed from abnormal at baseline to normal: overweight, obesity, prediabetes, hyperlipidemia and elevated blood pressure.

(The reversal of overweight or obesity is defined according to references .

For subject with general obesity at baseline: weight loss of 1.5 kg after intervention;

For subject with central obesity at baseline: waist circumference reduction of 1.5 cm after intervention.)

Time Frame:

From the baseline (the first day of the intervention phase) to the 14th day of the intervention phase.

### **2.2.2. Secondary outcomes**

- Change in insulin measurements from fasting blood sample. (Time Frame: from the baseline (the first day of the intervention phase) to the 14th day of the intervention phase.)
- Change in insulin-like growth factor-1 from fasting blood sample. (Time Frame: from the baseline to the 14th day of the intervention phase.)
- Change in mean blood glucose. (Time Frame: from the baseline to the 14th day of the intervention phase.)
- Change in gut microbial compositions. (Time Frame: from the baseline to the 14th day of the intervention phase.)
- Change in body weight (kg). (Time Frame: from the baseline to the 14th day of the intervention phase.)
- Change in body weight (kg). (Time Frame: from the baseline to the 14th day of the self-maintenance phase.)
- Change in waist circumference (cm). (Time Frame: from the baseline to the 14th day of the intervention phase.)

- Change in waist circumference (cm). (Time Frame: from the baseline to the 14th day of the self-maintenance phase.)

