### **3.3. Interventions**

#### **3.3.1. Experimental arm:**

##### **Intermittent caloric restriction**

The experimental intervention is based on the 5:2 diet, which involves caloric restriction for 2 days (consecutive or nonconsecutive, 600 kcal/d for male and 500 kcal/d for female) per week and unrestricted eating during the other 5 days of the week. Total trial duration is one month consisting of a 14-day intervention phase and a 14-day self-maintenance phase. During the maintenance phase, two follow-up electronic questionnaires were conducted.

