### **3.4. Randomisation**

Randomisation is stratified by two age groups and with block size of 2 and allocation of 1:1 at each stratum. The randomisation was done by Stata software version 15. For each stratum a sequence of subjects IDs and intervention allocations was generated, which by creating a random variable and ordering on that variable. After signing the informed consent form, the subjects are assigned to the experimental or the control groups and receive the designed intervention.

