### **5.2.2. Analysis of continuous outcomes**

The continuous outcome will be summarised using number of subjects (n), mean, standard deviation (SD), minimum, and maximum by intervention group, and will be analysed by a GLM model with treatment as fixed effect and with normal distribution and identity link function. Difference in mean outcome and mean differences with their two-sided 95% confidence intervals between two groups will be derived from the GLM model.

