## 8. Study variable list

NO	Variables	
	Baseline	
1	Name	T
2	Sex	B
3	Recruited date	D
4	Birth date	D
5	Height	N
6	Weight	N
7	Waist circumstance	N
8	Age	N
9	Family history of cardiovascular disease	B
10	Fasting blood glucose (mmol/L)	N
11	OGTT 2-hours glucose (mmol/L)	N
12	Glycosylated hemoglobin	N
13	Fasting insulin (mIU/L)	N
14	Total cholesterol (mmol/L)	N
15	Triglyceride (mmol/L)	N
16	High density lipoprotein (mmol/L)	N
17	Low density lipoprotein (mmol/L)	N
18	Systolic pressure (mmHg)	N
19	Diastolic pressure (mmHg)	N
20	Insulin-like growth factor-1	N
21	Gut microbial compositions	N
	Dietary intake	
22	Record date ( during 14-days intervention period )	D
23	Energy (kcal/d)	N
24	Protein (g/d)	N
25	Fat (g/d)	N
26	Carbohydrate (g/d)	N
	Continuous glucose monitoring	
27	Record date ( during 14-days intervention period )	D
28	24-hour average blood glucose	N
	At the 14th day after the dietary intervention phase	
29	Weight	N
30	Waist circumstance	N
31	Fasting blood glucose (mmol/L)	N
32	OGTT 2-hours glucose (mmol/L)	N
33	Fasting insulin (mIU/L)	N
34	Total cholesterol (mmol/L)	N
35	Triglyceride (mmol/L)	N

NO	Variables	
36	High density lipoprotein (mmol/L)	N
37	Low density lipoprotein (mmol/L)	N
38	Systolic pressure (mmHg)	N
39	Diastolic pressure (mmHg)	N
40	Insulin-like growth factor-1	N
41	Gut microbial compositions	N
	At the 14th day after the self-maintenance phase	
42	Weight	N
43	Waist circumstance	N
44	Self-reported dietary adherence	B
45	Psychological and symptoms during dietary intervention	B

Note: T, text variable; D, The date type; N, Continuous variable; B, binary variable.

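### Change in mean blood glucose has no listed pre-diet value: the only averaged glucose is recorded during the intervention, so the change can start or end on a diet day

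*SAP*

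**What the plan says.** SAP section 2.2.2 includes "Change in mean blood glucose. (Time Frame: from the baseline to the 14th day of the intervention phase". The same list ties insulin and IGF-1 to a fasting sample (for example, "Change in insulin-like growth factor-1 from fasting blood sample"), but the glucose item names no sample, device or variable. Section 2.1.2 starts the comparisons at "the baseline (the first day of the intervention phase".

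In SAP section 8, the baseline block holds fasting glucose, OGTT 2-hour glucose and glycosylated hemoglobin (variables 10-12). The day-14 block holds fasting and OGTT glucose (variables 31-32). Neither block holds a mean. The only average is variable 28, "24-hour average blood glucose", listed under continuous glucose monitoring with record dates "during 14-days intervention period".

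Section 3.3.1 gives the experimental arm 2 restricted days per week, and section 3.3.2 gives the control arm 7 low-carbohydrate days out of 14. Both allow consecutive or separate days, and neither says which days. On trial structure, section 3.3.1 states: "Total trial duration is one month consisting of a 14-day intervention phase and a 14-day self-maintenance phase". On the start, section 3.4 states: "After signing the informed consent form, the subjects are assigned to the experimental or the control groups and receive the designed intervention". No run-in is described. Continuous outcomes are analysed in section 5.2.2 by a "GLM model with treatment as fixed effect and with normal distribution and identity link function", with no further term.

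**The concern.** A change from baseline is meant to start from a value that the treatment has not yet touched. A fasting sample on the morning of day 1 precedes that day's eating. A 24-hour average on day 1 does not, and if day 1 is a diet day it already contains the diet.

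Two things follow. If an effect on glucose is present on diet days, it can enter either end of the subtraction, where it may cancel, shift the change or add noise, depending on where the diet days fall. And because the SAP does not say which monitoring days form each end, that choice is left to the analyst. What is at stake is the interpretation of one secondary outcome. The primary outcome is not touched, and fasting and OGTT glucose are listed at both times.

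**Working it through.** The plan states no figure on this point, so there is nothing to reproduce. The check compares the outcome definition with the variable list and then works out what a day-14-minus-day-1 change would contain.

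**1. Is there a listed pre-diet average?**

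| SAP section 8 block | Glucose variables | An average? |
|---|---|---|
| Baseline | Fasting, OGTT 2-hour, glycosylated hemoglobin | No mean glucose |
| Continuous monitoring | 24-hour average (variable 28) | Yes, intervention days only |
| Day 14 | Fasting, OGTT 2-hour | No |

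If variable 28 is the source, both ends of the change come from intervention days.

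**2. What the diet-day effect does to the change.** Let d_E and d_C be the unknown same-day effects of a diet day on the 24-hour average in the experimental and control arms. Let π₁ and π₁₄ be an arm's shares of subjects on a diet day on day 1 and day 14. The expected same-day contribution to the change is then

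(π₁₄ − π₁) × d in each arm.

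The arm contrast is free of a placement artefact only if these contributions are equal across arms, for example when π₁ = π₁₄ within each arm. Identical placement in both arms is not sufficient. With an illustrative π₁ = 60% and π₁₄ = 20% in both, the contributions are −0.4 d_E and −0.4 d_C, which differ unless d_E = d_C.

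**3. Possible placements.** The documents fix none, so π₁ and π₁₄ can each be 0% to 100%. If every control subject took days 1-7, that arm's contribution would be −d_C. If nobody had a diet day on day 1 or day 14, it would be 0. Two illustrations, both assumptions:

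| | Experimental | Control |
|---|---|---|
| Random days: π₁ = π₁₄ | 2/7 = 29% | 7/14 = 50% |
| Variance of (D₁₄ − D₁) | 2 × (2/7)(5/7) = 20/49 = 0.408 | 0.5 + 0.5/13 = 7/13 = 0.538 |
| Placement SD | 0.64 d_E | 0.73 d_C |
| One block, random start: π₁ = π₁₄ | 1/6 = 16.7% (a block each week) | 1/8 = 12.5% |
| Variance of (D₁₄ − D₁) | 2 × (1/6)(5/6) = 0.278 | 1/8 + 1/8 = 0.250 |
| Placement SD | 0.53 d_E | 0.50 d_C |

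D₁ and D₁₄ equal 1 on a diet day and 0 otherwise. In both illustrations π₁ = π₁₄, so the expected contribution is 0 and the harm is noise. That zero comes from the assumed placement, not from the documents.

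**4. Size of the noise.** Let s² be the day-to-day variance apart from diet status, assumed independent between days 1 and 14. The change has variance 2s² plus the placement variance times d². Under random placement the proportional increase is 0.408(d/s)²/2 and 0.538(d/s)²/2. With d/s = 0.5 this is 5% and 7%; with d/s = 1, 20% and 27%; with d/s = 2, 82% and 108% (experimental and control). The documents give neither d nor s.

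**5. A 14-day mean as the alternative.** Let t² be the between-person variance and r the correlation of baseline fasting glucose with a subject's mean. The adjusted mean has variance t²(1 − r²) + s²/14. With d = 0 and r = 0 it is noisier than the change once t²/s² exceeds 2 − 1/14 = 1.93.

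A mean also dilutes an effect that builds up. If the effect rises linearly from 0 on day 1 to full size on day 14, the mean captures (0 + 1 + … + 13)/(13 × 14) = 91/182 = one half. Its signal-to-noise ratio is then lower once t²/s² exceeds 2/4 − 1/14 = 0.43.

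**The case against.** **The link to variable 28 is inferred.** This stands. The SAP never equates mean blood glucose with the monitoring average, and day 14 minus day 1 is only one natural reading. But if another source was meant, the SAP still has to name it.

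**Day 1 may have been pre-diet in practice, or an earlier recording may exist.** A reader might infer that no pre-diet monitoring took place. The documents do not establish that. The Protocol document is essentially the ethics approval; it ticks a protocol among the papers considered, and monitoring times could be stated there. What can be said is that the SAP lists no pre-diet average and describes no period that would supply one.

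**The arm comparison may be unbiased.** A reader might infer that the contrast is biased because the arms have different numbers of diet days. That does not follow: random placement gives 29% against 50% on day 1 and still no expected shift, because each share is the same on day 14. The opposite shortcut, that bias needs placement to differ by arm, also fails (working, step 2).

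**It is a minor outcome.** This stands, and it limits the weight of the point.

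**Conclusion.** The point holds as a gap in definition. As written, the SAP permits a change whose starting or ending value is taken on a diet day, and it lists no average that could serve as a pre-diet baseline. This rests on variable 28 being the source and on the change being day 14 minus day 1.

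The effect on each arm's change is (π₁₄ − π₁)d, which can lie anywhere from −d to +d because placement is not fixed. In the two illustrations the expected shift is nil and the placement SD is 0.50 to 0.73 of the same-day effect. No size in mmol/L can be given. The documents do not show that bias occurred, nor that a 14-day mean would be more precise. Severity is low: one secondary outcome in a pilot.

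**What to change.** - In section 2.2.2, name variable 28 as the source if that is what is meant, and do not treat a day-1 average that may include the diet as a pre-diet baseline.
- If a pre-diet average was recorded, add it to the baseline block of section 8 and use it as the start of the change. State which monitoring days form the other end.
- If none exists, reword secondary objective 3 in section 2.1.2 and the outcome in section 2.2.2 as a comparison of mean glucose during the intervention. Fix in advance which recorded days enter (all intervention days, or a defined late window) and the minimum number of recorded days.
- In either case, add baseline fasting glucose (variable 10) and the randomisation age stratum (section 3.4) to the section 5.2.2 model, and report recorded days by arm. Glycosylated hemoglobin (variable 12) is an alternative covariate; it is not listed at day 14, so it cannot form a change.
- Do not adjust for diet-day status. It arises after randomisation and is part of the treatment.

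**Cost.** No new data are needed. Without a pre-diet average, however, the quantity is no longer a within-person change. The mean keeps between-person variance, and a full 14-day mean dilutes an accumulating effect (working, step 5). No precision gain over the change is claimed, and the choice of window is the sponsor's. Merely naming the source and the days at each end would remove the ambiguity, but a day-1 average that may include the diet would still serve as baseline.

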### **2.2.3. Case ascertainment and case definitions**

#### **(1) Cardiometabolic abnormalities**

- ① Overweight or obesity (central obesity or general obesity)
- ② Prediabetes: impaired fasting glucose (IFG) and/or impaired glucose tolerance (IGT)
- ③ Dyslipidemia
- ④ Elevated blood pressure

#### **Definitions for cardiometabolic abnormalities:**

##### **① Overweight or obesity**

- For subjects ( $9 \leq \text{age} \leq 18$  years) :
  - General obesity: Body mass index higher than the 85th percentile for overweight and the 90th percentile for obesity, based on the references for screening overweight and obesity in Chinese children and adolescents.
  - Central obesity: Waist circumference higher than the 90th percentile of the age and gender-specific reference for screening cardiovascular risk factors in Chinese children and adolescents.
- For subjects ( $19 \leq \text{age} \leq 30$  years) :
  - General obesity: Body mass index between 24.0 and 27.9 kg/m^2 for

overweight and  $\geq 28$  kg/m^2 for obesity.

- Central obesity: Waist circumference  $\geq 85$ cm for men and  $\geq 80$ cm for female. Based on recommendation of overweight and obesity in Chinese adults.

## ② **Prediabetes:**

With IFG and/or IGT. IFG: fasting glucose from 5.6 to 6.9 mmol/L; IGT: 2-h glucose in the 75g oral glucose tolerance test from 7.8 to 11.0 mmol/L.

Based on recommendation of American Diabetes Association.

## ③ **Dyslipidemia:**

- For subjects (9  $\leq$  age  $\leq$  18 years) :

Triglycerides of  $\geq 1.70$  mmol/L or total cholesterol of  $\geq 5.18$  mmol/L or lowdensity lipoprotein cholesterol  $\geq 3.37$  mmol/L or highdensity lipoprotein cholesterol of  $\leq 1.04$  mmol/L. Based on recommendation in Chinese children and adolescents.

- For subjects ( 19  $\leq$  age  $\leq$  30 years) :

Triglycerides of  $\geq 1.7$  mmol/L or total cholesterol of  $\geq 5.2$  mmol/L or lowdensity lipoprotein cholesterol  $\geq 3.4$  mmol/L or highdensity lipoprotein cholesterol of  $\leq 1.0$  mmol/L. Based on guideline for the management of dyslipidemia in Chinese adults.

**④ Elevated blood pressure:**

- For subjects ( $9 \leq \text{age} \leq 18$  years) :

Blood pressure higher than the 90th percentile of blood pressure age and gender-specific reference standards for Chinese children and adolescents, or blood pressure  $>120/80$  mmHg.

- For subjects ( $19 \leq \text{age} \leq 30$  years) :

Systolic blood pressure  $\geq 120$  mmHg and/or diastolic blood pressure  $\geq 80$  mmHg. Based on Chinese guidelines for the management of hypertension.

### **3. Study Design**

#### **3.1. Design**

This study is a randomized controlled pilot trial to compare the effects of intermittent caloric restriction versus low carbohydrate diet on cardiometabolic risk factors in youth.

#### **3.2. Trial Sites**

The trial is conducted in Shanghai, China.

### **3.3. Interventions**

#### **3.3.1. Experimental arm:**

##### **Intermittent caloric restriction**

The experimental intervention is based on the 5:2 diet, which involves caloric restriction for 2 days (consecutive or nonconsecutive, 600 kcal/d for male and 500 kcal/d for female) per week and unrestricted eating during the other 5 days of the week. Total trial duration is one month consisting of a 14-day intervention phase and a 14-day self-maintenance phase. During the maintenance phase, two follow-up electronic questionnaires were conducted.

#### **3.3.2. Control arm:**

##### **Low carbohydrate diet**

During the 14-day intervention period, the subjects receive 7 days (consecutive or nonconsecutive) of low carbohydrate diet intervention. Carbohydrate intake of low-carbohydrate diet should be controlled as  $\leq$  50g per day. Total trial duration is one month consisting of a 14-day intervention phase and a 14-day self-maintenance phase. During the maintenance phase, two follow-up electronic questionnaires were conducted.

#### **3.3.3. Additional health care: health education on reducing the cardiometabolic risk**

Health education is conducted once a week during 14-day dietary intervention for all subjects. Health education including the understanding of cardiovascular disease, how to determine the cardiometabolic risk level, and the lifestyle intervention as caloric restriction and increased physical activity to promote health.

### **3.4. Randomisation**

Randomisation is stratified by two age groups and with block size of 2 and allocation of 1:1 at each stratum. The randomisation was done by Stata software version 15. For each stratum a sequence of subjects IDs and intervention allocations was generated, which by creating a random variable and ordering on that variable. After signing the informed consent form, the subjects are assigned to the experimental or the control groups and receive the designed intervention.

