## **5. Statistical Analyses**

### **5.1. Primary Outcome Analysis**

#### **5.1.1. ITT analysis of the primary outcome - the primary analysis**

The primary outcome is a binary composite outcome: occurrence of reversal outcome from any cardiometabolic abnormality at the 14th day after dietary intervention phase. The primary analysis will be based on the ITT population as defined above.

The primary endpoint will be summarised by number (%) of subjects that have reverse cardiometabolic abnormality by groups. Statistical analysis will be performed as a two-sided test, using chi-square test for detecting group difference of the percentage. If any subjects dropped off from the

primary endpoint, modified ITT analysis will be performed by using the available subjects.

A generalised linear model (GLM) will be used. In the GLM model, the occurrence of reversal outcome from any cardiometabolic abnormality at the 14th day after intervention phase will be treated as the response variable following a binomial distribution, the treatment as fixed effect and logit link function will be used. From this model, the reversal rate difference and its 95% CIs between two groups will be estimated.

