### **Covariate adjusted analysis of the primary outcome**

An analysis of the primary endpoint will be adjusted for age, sex, family history of cardiovascular disease, and fasting insulin concentrations at baseline by GLM model. The model may not converge when all covariates are introduced into the model simultaneously. If this occurs, a covariate will be removed from model one by one starting from the last covariate until the model converges.

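### SAP 3.4's fixed blocks of 2 in each age stratum force every second allocation, if the list was built in pairs as stated: an avoidable selection risk, not evidence of steering

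*SAP*

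**What the plan says.** SAP 3.4 sets the rule: "Randomisation is stratified by two age groups and with block size of 2 and allocation of 1:1 at each stratum". On how the list was made it says "The randomisation was done by Stata software version 15", and that a sequence was produced for each stratum, "which by creating a random variable and ordering on that variable". It does not say whether the sorting was within pairs or across the whole stratum. On timing: "After signing the informed consent form, the subjects are assigned to the experimental or the control groups". The supplied text describes no method of concealing the list and no rule on keeping the block size undisclosed.

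SAP 3.3.1 and 3.3.2 describe a 5:2 caloric restriction diet and a low carbohydrate diet. The documents never use the term open-label, but participants and the staff who deliver such diets would know which one was given.

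Entry needs at least one cardiometabolic abnormality (Protocol, adjusted inclusion criteria). The primary endpoint in SAP 2.2.1 counts subjects with "at least one reverse of cardiometabolic abnormalities". Within that definition, general obesity reverses on weight and central obesity on waist circumference, so they are two separate routes to success, although SAP 2.2.3 lists them as one category.

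The primary model in SAP 5.1.1 has "the treatment as fixed effect and logit link function will be used", with no covariates. The adjusted analysis is "adjusted for age, sex, family history of cardiovascular disease, and fasting insulin concentrations at baseline". If it fails to converge, "a covariate will be removed from model one by one starting from the last covariate until the model converges".

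**The concern.** In a 1:1 block of two, the first assignment dictates the second. A person who knows the block size and has followed a stratum therefore knows the next arm half of the time before approaching the next candidate. Assignment after consent does not remove this exposure, because the choice of whom to approach, and when, comes before consent.

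The endpoint gives such a choice some leverage. A candidate with two abnormalities has two routes to success and a candidate with one has one route. If candidates with more routes went preferentially to one arm, the difference in reversal rates would shift without any effect of diet. The primary chi-square test and model would not correct for this, and the adjusted model does not include the number of abnormalities.

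**Working it through.** The plan gives no figure on predictability, so there is none to reproduce.

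**1. Predictability under the stated rule.** Inputs: block size 2 and 1:1 within stratum (SAP 3.4). Only AB and BA exist.
- Share of allocations that are certain: 1/2 = 50%.
- Expected correct guesses: 0.5 × 0.5 + 0.5 × 1 = 75%. Simple randomisation gives 0% and 50%.

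**2. Knowing the position in the pair.** It follows from counting from the first subject in the stratum. It can also be inferred: the two members of a pair always differ, so two equal consecutive assignments must straddle a pair boundary. The chance of at least one such event in m pairs is 1 − 0.5^(m−1): 50% for m = 2, 87.5% for m = 4, 93.75% for m = 5. Someone who sees only the single last assignment in the stratum has no certain allocation, but guessing the opposite is still right 0.5 × 1 + 0.5 × 0.5 = 75% of the time.

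**3. Larger blocks.** Fixed sizes are enumerated. The mixed row is simulated (4,000 sequences of 40 allocations; the guesser knows the possible sizes and the full history, but not the current size).

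| Blocks | Certain | Guessable |
|---|---|---|
| 2 (stated) | 50% | 75% |
| 4 | 33.3% | 70.8% |
| 6 | 25% | 68.3% |
| 4 or 6 at random | about 6% | about 69% |

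**4. Illustrative bias.** Assumptions: each abnormality reverses with probability p; reversals within a person have correlation r; there is no diet effect.
- Gap between two abnormalities and one: [2p − p² − r·p(1−p)] − p = p(1−p)(1−r).
- Suppose a fraction f of forced slots is steered, with two-abnormality candidates sent to one arm and one-abnormality candidates to the other. Forced slots are half of each arm, so bias = 0.5 × f × gap.

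| p | Gap, r = 0 | Gap, r = 0.5 | Bias, r = 0.5, f = 1 | Bias, r = 0.5, f = 0.25 |
|---|---|---|---|---|
| 0.1 | 9 | 4.5 | 2.3 | 0.6 |
| 0.2 | 16 | 8 | 4.0 | 1.0 |
| 0.3 | 21 | 10.5 | 5.3 | 1.3 |

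All entries after p are percentage points. Independence (r = 0) is the high end, since weight and waist may well move together; with f = 1 the bias would then be 4.5, 8.0 or 10.5 points.

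**5. Can the retained list settle whether pairs were used?** If a stratum were one shuffle of k + k allocations, the chance that all k consecutive pairs hold one of each arm is 2^k / C(2k, k): 32/252 = 12.7% for k = 5, 1,024/184,756 = 0.55% for k = 10. About ten pairs in a stratum are enough.

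**6. Precision.** Assumed N = 40, 60 or 80 and 50% reversal. The 95% CI half-width is 1.96 × √(2 × 0.25/(N/2)) = 31.0, 25.3 or 21.9 points. Restricting to first-in-pair halves N and multiplies the standard error by √2 = 1.41, giving 43.8, 35.8 or 31.0 points.

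**The case against.** The best defence is that predictability does harm only if someone can use it. The supplied protocol is an ethics-approval summary and some pages are not in the supplied text, so concealment may be described elsewhere. Nothing shows that recruiters knew the block size. Nor is it shown that they knew a candidate's full set of abnormalities before approach: weight, waist and blood pressure are easily seen, but the glucose tolerance test and lipids need testing. The sorting sentence may mean a whole-stratum shuffle, in which case the pairs do not exist. Larger blocks alone lower guessing only from 75% to about 69%. In a pilot, an illustrative bias of 0.6 to 5.3 points is small beside assumed half-widths of 22 to 31 points.

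These arguments stand as limits on severity. They do not remove the mechanism: the stated rule forces half of the allocations, and the fall in certain allocations from 50% to about 6% is real.

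A reader might infer more: that recruitment was steered, that there was no concealment, or that the primary comparison is invalid. The documents support none of these. They are silent on who held the list and on what recruiters knew, and they give no recruitment data from which steering could be seen.

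**Conclusion.** The concern holds as a conditional design risk that should be addressed; it is not a fatal flaw. If the list was built in pairs as SAP 3.4 states, 50% of allocations are certain and 75% guessable to someone who knows the block size and the stratum history. That part is arithmetic. Whether anyone was placed to exploit it is unknown.

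The bias figures rest on assumed reversal rates, correlation and steering fractions, and the precision figures on assumed sample sizes. They show the order of magnitude and are not estimates for this trial. If the list proves to be a whole-stratum shuffle, the forced-pair argument falls away and what remains is an incorrect statement of the block size.

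**What to change.** (a) **For anyone not yet randomised:** in each stratum, replace the fixed block of 2 with randomly varying larger blocks (for example 4 and 6), keep the sizes undisclosed, and hold the list away from recruiters. Larger blocks help mainly in combination with a hidden list. Cost: a new list, and an end imbalance of up to 3 per stratum instead of 1. The past tense in SAP 3.4 suggests that this may no longer apply.

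(b) **If allocation is complete:** check the retained list.
- If it was in pairs, add to SAP 5.1 a table of the number of baseline routes to reversal by arm and position in pair. Count general overweight/obesity and central obesity separately, as the reversal definition in SAP 2.2.1 does, plus prediabetes, dyslipidemia and elevated blood pressure (0 to 5). The four-category list in SAP 2.2.3 would hide a participant who has both obesity routes. A first-in-pair analysis of the primary outcome may be added, but it is descriptive only and could not detect a bias of the size illustrated.
- If it was not in pairs, correct the block-size statement in SAP 3.4.

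(c) **Adjusted model:** add the 0 to 5 count, in the order age, sex, route count, family history, fasting insulin, so that the drop-from-last rule removes two other covariates first. Fix this before outcomes are reviewed by arm, or label it post hoc. It reduces imbalance on this count only, not steering on unrecorded traits such as motivation. The primary analysis is unchanged.

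(d) **If concealment cannot be shown,** state the predictability as a limitation.

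Items (b) and (c) cost the retained list, one table and one or two model runs. SAP section 8 already lists the baseline measurements needed for the count and the date of recruitment, but no sequence number or position in pair, so these must come from the list.
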